### **Follow up of study participants**

As required by the FDA, study patients will be followed long term (up to 15 years) and the PI will continue to report data and safety concerns to the FDA, DSMC, and IRB as they arise during this follow-up period.

---

## **8.0 Agent Information and Risks**

### **8.1 HB1.F3.CD. NSCs (IND # 14041)**

#### **8.1.1 Animal Toxicity Data**

All toxicity studies to date in mice have shown no evidence of organ damage or tumorigenicity due to NSCs. Please see sections 2.4.2 and 2.4.3.

#### **8.1.2 Human toxicity data**

See sections 2.5.1 and 6.2.2.

#### **8.1.3 Administration**

Intracranial administration—either through direct injection into tumor at the time of surgery or via a Rickham.

#### **8.1.4 Supplier**

City of Hope

## 8.2 5-Fluorocytosine (5-FC, Flucytosine, Ancobon; NSC # 103805)

### 8.2.1 Description

5-FC is classified as an antifungal agent. It is a fluorinated pyrimidine analog structurally related to 5-FU and floxuridine. It is a white to off-white crystalline powder. 5-FC is available in 250 mg and 500 mg capsules. The capsules also contain cornstarch, lactose and talc.

### 8.2.2 Chemical Name

4-Amino-5-fluoropyrimidin-2(1*H*)-one

Molecular Formula C4H4FN3O

Molecular weight 129.09

### 8.2.3 Human Toxicity

See section 6.2.4.1

### 8.2.4 Pharmacokinetic Data

5-FC is rapidly and well absorbed. Its oral bioavailability is 78-90%. There is no significant systemic metabolism of 5-FC. More than 90% is excreted by glomerular filtration as unchanged drug. The systemic half-life is 2.5 to 6 hours. The time to peak concentration is 1-2 hours. Distribution: 5-FC distributes widely in body water. Less than 4% is protein-bound. Levels in the cerebrospinal fluid are approximately 80% of serum levels.

### 8.2.5 Administration

The dose of 5-FC will be given orally every 6 hours for 7 days following each dose of NSCs (i.e. on days 4-10 and 18-24 of every 28 day cycle). The dose will be rounded to the nearest 250 mg. Administer a few capsules at a time over a 15-minute period to minimize nausea and vomiting.

### 8.2.6 Storage and Stability

Store between 15 and 30 °C in a tight, light-resistant container

### 8.2.7 Supplier

Commercially available; provided by the study.

## 8.3 Leucovorin

### 8.3.1 Description

Leucovorin Calcium Tablets contain either 5 mg or 25 mg leucovorin as the calcium salt of *N*-[4-[[2-amino-5-formyl-1,4,5,6,7,8-hexahydro-4-oxo-6-pteridinyl]-methyl]amino]benzoyl]-*L*-glutamic acid. This is equivalent to 5.40 mg or 27.01 mg of anhydrous leucovorin calcium (leucovorin calcium (leucovorin calcium tablets) tablets). In addition each tablet contains the following inactive ingredients: colloidal silicon dioxide, croscarmellose sodium, lactose monohydrate, magnesium stearate, and microcrystalline cellulose. The 25mg tablet also contains D&C yellow no. 10 and FD&C blue no. 1.

### 8.3.2 Chemical name

*N*-[4-[[2-amino-5-formyl-1,4,5,6,7,8-hexahydro-4-oxo-6-pteridinyl]-methyl]amino]benzoyl]-*L*-glutamic acid

Molecular formula C20H21CaN7O7

Molecular weight: 511.51

**8.2.8 Human toxicity data** see section 6.2.4.2**8.2.9 Pharmacokinetic data**

Absorption: Tmax, oral: 1.72 to 2.3 hr; oral bioavailability: 97% (25 mg); 75% (50 mg); 37% (100 mg)

Metabolism: Hepatic and intestinal mucosa: extensive

Elimination Half Life: total reduced folates: (oral) 3.5 to 5.7 hr

**8.2.10 Administration**

Orally once a day for 7 days

**8.2.11 Storage and stability**

Store at 20° to 25° C (68° to 77° F). Dispense in a tight, light-resistant container. Protect from light and moisture.

**8.2.12 Supplier**

Commercially available; provided by the study.

**8.4 Missed or skipped doses of 5-FC (with Leucovorin)**

If the participant misses or skips doses of 5-FC or leucovorin, those doses can be made up.

---

**9.0 Correlative/Special Studies****9.1 Immunological Correlative Studies**

In order to assess for possible development of anti-NSC T cell and antibody responses with repeat exposure to the NSCs, blood samples from study patients will be collected for isolation and storage of PBMCs and serum prior to the start of study treatment, on day 15 of cycle 1, days 1 and 15 of cycle 2, and then on day 15 of subsequent cycles (please see section 9.1.5 for further details). We will also be assessing study patients for peripheral persistence of the NSCs (section 9.1.5.1) and testing for replication competent retrovirus (RCR) (section 9.1.6).

The following studies, which have been successfully performed in our first neural stem cell study of CD-expressing NSCs and oral 5-FC, will be done by the City of Hope Clinical Immunobiology Correlative Studies Laboratory (COH CICSL).

**9.1.1 Assessment of the development of anti-NSC T cell responses**

Development of a T cell response to the NSCs will be evaluated by a combination of TcR V $\beta$  spectratyping and CD107 degranulation assays using established laboratory SOP and protocols. Briefly, V $\beta$  spectratyping of patient PBMCs collected prior to and after NSC administration will identify unique clonal populations of T cells that have expanded post-NSC administration.

Such expanded populations have the potential to be specific for and to eliminate the administered NSCs. The specificity of the clonally-expanded T cells for the NSCs will be evaluated by 1) incubating pre- and post-infusion PBMC samples with the NSCs, followed by flow cytometric analysis using commercially available monoclonal antibodies specific for the identified clonotypes to determine the candidate T cells and 2) assessing surface CD 107 (a measure of cytotoxicity) on the surface of those T cells.

**9.1.2 Determination of development of antibody responses to the NSCs.**

An evaluation of humoral responses to NSCs will be performed in the CICSL by flow cytometric evaluation of antibody binding to NSCs. Briefly, aliquots of cultured NSCs will be incubated on ice with cryopreserved patient serum samples that have been heat treated to inactivate complement. Following incubation the NSCs will be washed and bound antibodies detected using a secondary goat anti-human Fc antibody conjugated to FITC. After a second

washing step, the NSCs will be analyzed by CICSL staff using a flow cytometer in the COH Analytical Cytometry Core. Binding of human antibodies to the NSCs will be detected as a shift in the mean fluorescence intensity (MFI) compared to NSCs not treated with human serum. All samples obtained from individual subjects prior to and after therapy will be evaluated in parallel to evaluate possible development of humoral anti-NSC responses over time. The statistical significance of any detected MFI shifts will be evaluated by comparison with data from the NSC binding of a reference panel of normal human sera. The assay will include as a control the parental NSC (not transduced with the CD gene) to evaluate whether antibody responses are directed against the CD gene product.

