### 2.1 Introduction

[figure not shown]
High-grade gliomas are difficult to treat due to their relative resistance to chemotherapy and radiation, as well as their highly invasive nature. Human neural stem cells (NSCs), modified to express a therapeutic transgene, hold great promise for brain tumor therapy due to their inherent tumor-tropic properties and potential use as vehicles for delivering chemotherapy directly to infiltrating glioma cells in the brain. Data from animal models have demonstrated the safety and efficacy of NSCs for tracking to invasive tumor cells as well as to distant micro-tumor foci and delivering therapeutic gene products to tumor cells. Our recently completed first-in-human pilot study of cytosine deaminase (CD)-expressing NSCs given in combination with oral 5-fluorocytosine (5-FC) has shown that treatment with one dose of NSCs followed by a 7-day course of 5-FC in recurrent high-grade glioma patients is safe and feasible.

NSCs can overcome obstacles of drug-delivery that limit current gene therapy strategies and provide an effective anti-tumor response. In this phase I clinical trial we will use the same *v-myc*-immortalized human NSC line (HB1.F3.), retrovirally transduced to express CD (HB1.F3.CD NSCs), ([name] et al., 2000) as was used in our first-in-human pilot study. This HB1.F3.CD NSC line has been well-characterized, favorably reviewed by the NIH RAC, and established as a Master Cell Bank at the COH Center for Biomedicine & Genetics.

After intracranial administration to patients with recurrent brain tumors, we hypothesize that, based on pre-clinical data, CD-expressing NSCs will distribute throughout the primary tumor site as well as co-localize with infiltrating tumor cells within 3 days of administration. Study patients will then take oral 5-FC and leucovorin for 7 days. The CD-expressing NSCs will locally convert 5-FC to 5-FU (Figure 1), and the 5-FU will diffuse out of the NSCs at tumor sites, thereby generating concentrated cytotoxicity at sites of tumor in the brain. This CD/5-FC prodrug strategy is known to have a large bystander effect. (Huber et al., 1994; Barresi et al., 2003).

Based on the safety data obtained in the pilot feasibility study in patients with recurrent high-grade gliomas who received only round of study treatment, in this phase I study we will assess the safety and feasibility of administering repeat doses of NSCs followed by 7-day course of 5-FC and leucovorin.

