After the first dose, the NSCs will be administered through a Rickham catheter via convection enhanced delivery.

**Figure 1.** NSCs expressing the enzyme *E. coli* cytosine deaminase migrate to tumor sites. The inactive oral prodrug, 5-FC, crosses the blood-brain barrier and is converted to the active cytotoxic drug 5-FU by CD-expressing NSCs.

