##### 2.5.3.1.2 Evaluation of humoral responses

Blood samples were obtained prior to surgery, and on days 32 and 60 to look for evidence of development of anti-NSC antibodies in patients' sera by flow cytometric evaluation of antibody binding to NSCs. Data from patients in dose levels 1 and 2, as well as the first 4 patients in dose level 3, show no detection of anti-NSC antibodies outside the normal range after first exposure (Portnow et al., 2013a).

**Figure 7. Results of anti-NSC antibody testing.** Normal donor sera: n=10. Each data point for normal sera represents the mean of 5 independent experiments. Each data point for study patients' sera represents the mean of triplicate assays. The dotted lines indicate a "normal mean fluorescence intensity (MFI)" range of 0.55 to 2.59 that represents a 95% prediction interval based on a 2.3 standard deviation in each direction (Hahn and Meeker, *Statistical Intervals*, Wiley and Sons, 1991). The "positive control" is the mean of triplicate assays on serum from a patient who was determined to be ineligible for the study due to having an antibody to one of the HLA antigens (A1) on the NSCs.

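### As described in section 9.1.2, the antibody assay reads cell-surface binding, so similar MFI on CD-transduced and parental NSCs would not show that anti-CD antibodies are absent

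*Combined protocol and SAP*

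**What the plan says.** The antibody method is in section 9.1.2. The first step is that "aliquots of cultured NSCs will be incubated on ice with cryopreserved patient serum samples that have been heat treated to inactivate complement". Then: "Following incubation the NSCs will be washed and bound antibodies detected using a secondary goat anti-human Fc antibody conjugated to FITC". After a second wash the cells go to the flow cytometer, and a shift in mean fluorescence intensity (MFI) relative to cells without serum is the readout. Samples from before and after therapy are run in parallel, and shifts are judged against a reference panel of normal sera.

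The last sentence of the section adds the parental NSC line, which lacks the CD gene, as a control. Its stated purpose is "to evaluate whether antibody responses are directed against the CD gene product".

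On where CD acts, section 2.1 says that the NSCs convert 5-FC locally and that "the 5-FU will diffuse out of the NSCs at tumor sites". Nowhere do the documents describe CD as secreted or displayed on the membrane.

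Section 1.2.1 makes anti-NSC T-cell and/or antibody responses to repeat dosing a secondary objective. It does not single out CD.

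**The concern.** The parental control is given a specific job: to tell whether an antibody response is aimed at the CD protein. That works only if serum antibody can reach CD in the assay. The steps in section 9.1.2 expose the outer surface of the cell, whereas section 2.1 implies that the enzyme is inside. The contrast between the two lines would then come out about the same whether or not a patient has anti-CD antibody.

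What is at stake is the interpretation of a null result. CD is the bacterial transgene product, and repeat exposure to the NSCs is new in this trial. Of the immunological assays in section 9.1, this control is the only step that tries to attribute a response to CD. The T-cell section (9.1.1) has no parental-line arm. A reader of the results could take matching MFI on the two lines as reassurance about CD that the assay, as described, cannot give.

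**Working it through.** The plan gives no sample size, power or error rate for this control, so there is no figure to reproduce. The check sets the assay steps against the stated site of CD action.

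**Step 1: what the assay exposes.** Section 9.1.2 lists cultured cells, ice, complement-inactivated serum, wash, FITC-labelled secondary antibody, wash and cytometer. It describes no fixation, permeabilisation or lysis, no purified CD protein as target and no viability gate. Incubation on ice and complement inactivation both fit staining of live, intact cells. As written, this is a surface-binding assay.

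**Step 2: where the antigen is.** Section 2.1 has 5-FU diffusing out of the NSCs after conversion, which places the conversion inside the cell. This is an inference, but nothing in the documents points the other way.

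**Step 3: what has been shown to be detectable.** The positive control for this assay in the first study (section 2.5.3.1.2, Figure 7) came from a single screened individual, "who was determined to be ineligible for the study due to having an antibody to one of the HLA antigens (A1) on the NSCs". It shows that the assay can detect antibody to an HLA antigen on the NSCs. Neither study is described as having an anti-CD positive control.

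**Step 4: what the contrast would read.** This is an illustration, not a result from the plan. Let f be the fraction of CD-transduced assay cells whose interior the serum can reach, and D the MFI shift that anti-CD antibody causes in those cells. Assume a linear mixture and otherwise identical lines.

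- Anti-CD contribution to the CD-minus-parental difference = f × D.
- All cells intact: f = 0, so the contribution is 0 × D = 0 at any titre.

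Leaky or dead cells make f positive. The plan sets no threshold for the contrast, so as a yardstick I use the normal MFI range in Figure 7, 0.55 to 2.59.

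- Midpoint: (0.55 + 2.59) / 2 = 1.57.
- Half-width: (2.59 − 0.55) / 2 = 1.02.
- A serum starting at the midpoint leaves the range when f × D > 1.02.

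| Assumed f | D needed (1.02 / f) |
|---|---|
| 0 | never reached |
| 0.05 | 1.02 / 0.05 = 20.4 |
| 0.25 | 1.02 / 0.25 = 4.08 |

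The documents give no f for the cultured assay cells. Table 2 in section 2.7 shows viability of 75.2% to 79.9%, that is 20.1% to 24.8% non-viable, but for cells in the catheter-delivery experiment. The values of f above are therefore assumptions. They show that any anti-CD signal would depend on an uncontrolled quantity. If the two cultures differed in their share of leaky cells, a spurious difference between the lines could also appear.

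**The case against.** The strongest objection is that this rests on silence in a summary. Section 9.1.2 introduces the method as a brief account, the laboratory SOP is not in the documents, and section 9.1 says these studies were performed successfully in the first trial. That stands as a limit on certainty: the SOP may contain a step that the summary omits. Past success does not settle it, because the positive control shown was an anti-HLA serum.

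The location of CD is also inferred. The Figure 1 caption, "NSCs expressing the enzyme", names no compartment, and only the diffusion statement in section 2.1 supports the inference. That is fair, though no alternative location is offered.

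A third objection is that little depends on this control. The objective concerns anti-NSC responses in general. The MFI shift, the pre/post comparison and the normal-sera reference do not use CD attribution. Surface antibody is arguably the kind that matters most for recognition of living cells, and T-cell responses are tested separately in section 9.1.1. Section 13.3.4 makes these data exploratory and descriptive, and section 5.3.1 does not tie treatment stopping to antibody levels. All of this stands and confines the point to one sentence.

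A reader might also infer that the trial will report equal MFI as absence of anti-CD antibody. The plan contains no such rule and says nothing about how equal MFI will be read. The gap is that nothing prevents that reading while the stated purpose of the control invites it.

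**Conclusion.** The point holds in a narrow form. With the steps described, the CD-versus-parental comparison cannot do its stated job on intact cells, and similar MFI on the two lines would not be evidence against anti-CD antibody. This applies to every serum for which the comparison is used. No sample size, error rate or primary endpoint changes.

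It rests on two assumptions: that the laboratory does not permeabilise the cells, and that CD is intracellular, as section 2.1 implies.

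Two stronger readings are tempting, and the documents do not support them. One is that the control must read negative by construction: leaky or dead cells could give some signal, and the SOP has not been seen. The other is that the antibody part of secondary objective 1 fails: detection of antibodies to surface antigens such as HLA, and the general anti-NSC readout, are intact. Only attribution to the CD gene product is lost. Nor can the non-viable fraction in Table 2 be carried over to the assay cells, so the documents allow no numerical estimate of the assay's sensitivity to anti-CD antibody.

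**What to change.** Check the laboratory SOP first. If the cells are permeabilised, say so in section 9.1.2.

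If they are not:

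1. Replace the last sentence of section 9.1.2 so that the parental line is described as a comparator for surface-binding antibody only.
2. State that equal MFI on the two lines will support no conclusion about the presence or absence of anti-CD antibody.
3. Exclude dead cells from the MFI by a viability gate.

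The first two are wording changes. The third is a small change to the cytometry procedure. None needs extra blood or visits.

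Optionally, if the sponsor wants to address anti-CD antibody, the serum aliquots stored under section 9.1.5.2 could be tested in a permeabilised condition on the same pair of lines, or in a binding assay on CD protein. Either would need its own normal-sera reference range, since the one in Figure 7 came from 10 donors under the existing assay, and an anti-CD positive control. The cost is added laboratory work and assay qualification, which is more than one further staining tube per sample.

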#### **9.1.3 Evaluation of the peripheral persistence of NSCs using quantitative PCR with *vMyc* primers**

An evaluation of the peripheral persistence of NSCs will also be performed in the CICSL by quantitative PCR using established laboratory SOP and primer pairs specific for the *v-myc* gene. Briefly, a standard curve will be generated using DNA isolated from the administered NSCs titrated into DNA from PBMCs (negative for *v-myc*); in parallel reactions, DNA isolated from patient samples will be subjected to amplification. The % NSC DNA (i.e. the % of total nucleated cells in samples that contain *v-myc* DNA) in patient PBMC samples will be determined from the standard curve. A parallel set of amplification reactions using genomic p21 primers (amplifying equivalently from all samples) will be used to normalize across samples.

#### **9.1.4 Assessment of serum cytokine levels in the event that a patient develops a suspected immune response to the NSCs**

The Human Cytokine Thirty-Plex Antibody Bead Kit (Invitrogen, Camarillo, CA) will be used to analyze serum samples for 30 cytokines: epidermal growth factor (EGF); eotaxin; basic fibroblast growth factor (FGF-basic); granulocyte colony-stimulating factor (G-CSF); granulocyte macrophage colony-stimulating factor (GM-CSF); hepatocyte growth factor (HGF); interferon alpha (IFN- $\alpha$ ); IFN-gamma ( $\gamma$ ); interleukin-1 beta (IL-1 $\beta$ ); interleukin-1 receptor antagonist (IL-1RA); IL-2; interleukin-2 receptor (IL-2R); IL-4; IL-5; IL-6; IL-7; IL-8; IL-10; IL-12p40/p70; IL-13; IL-15; IL-17; IFN-  $\gamma$ -inducible protein 10 (IP-10); monocyte chemoattractant protein-1 (MCP-1); monokine induced by IFN-  $\gamma$  (MIG); monocyte inflammatory protein-1 alpha (MIP-1 $\alpha$ ); monocyte inflammatory protein-1 beta (MIP-1 $\beta$ ); regulated upon activation, normal T-cell expressed and secreted cytokine (RANTES); tumor necrosis factor (TNF)- $\alpha$ ; and vascular endothelial growth factor (VEGF). The assay plate will then be transferred to the Bio-plex HTF Luminex System (Bio Rad Laboratories, Inc., Hercules, CA) instrument for analysis. Cytokine concentrations will be calculated using Bio-plex Manager 3.0 Software with a 5 parameter curve-fitting algorithm applied for standard curve calculations for duplicate samples.

#### **9.1.5 Collection of blood samples for performing the immunological correlative studies**

**9.1.5.1** To assess for possible development of anti-NSC T cell responses and evaluate for peripheral persistence of the NSCs, approximately 30 ml of blood will be collected from each patient in lavender top tubes (liquid potassium EDTA) prior to the start of study treatment, on day 15 of cycle 1, days 1 and 15 of cycle 2, and then on day 15 of subsequent cycles. The samples will be sent to the City of Hope Clinical Immunobiology Correlative Studies Laboratory and processed, with PBMCs being isolated and stored according to established laboratory SOP.

**9.1.5.2** To assess for possible antibody responses, approximately 10 ml of blood will be collected from each patient in red top tubes (free of any anti-coagulant reagent) prior to the start of study treatment, on day 15 of cycle 1, days 1 and 15 of cycle 2, and then day 15 of subsequent cycles. The samples will be sent to the City of Hope Clinical

Immunobiology Correlative Studies Laboratory and processed to yield serum that will be frozen in several aliquots at -80°C.

**9.1.5.4** If a patient develops an adverse event that is suspected of being due to an immune response to the NSCs, 3-5 ml of blood will be collected in a red top tube at least twice (separated by approximately 2 days) during the event for analysis of serum cytokine levels via Luminex cytokine panels, as described in section 9.1.4.

#### **9.1.6 Collection of blood samples to perform RCR testing as part of long-term follow**

As per section 5.12, prior to surgery, at 3 months, 6 months, 1 year, and annually thereafter, at least 10 ml of blood will be collected from each patient in EDTA treated (lavender top) tubes and sent to CICSL. Samples will be processed with DNA being isolated and stored, according to established laboratory SOP, until RCR testing is performed by PCR.

All blood samples collected for the immunologic correlative studies as per section 9.1.5 and 9.1.6 will be sent to the COH CICSL.

